11.2 Cohort B

a. As a pilot study, Cohort B will use a single stage design with an accrual goal of 21 eligible patients. The anticipated accrual rate for Cohort B is 1 patient per month. Assuming an ineligibility rate of 20%, the study will accrue 26 total patients to enroll 21 eligible patients.

b. Primary Endpoint

The primary endpoint for Cohort B is complete response rate (CR). Given that Cohort B is intended as a pilot trial, we propose single stage design with the assumption that a true CR of 20% or higher indicates that the treatment is of considerable interest for patients with unresectable/metastatic DM whereas a true CR of 5% or lower indicates that the treatment will not be of further interest. Specifically, we will enroll 21 eligible patients with unresectable/metastatic DM. Three or more complete responses out of 21 would be considered evidence that the treatment warrants further study, provided other factors such as toxicity and overall survival also appear favorable. This design has an alpha of 8.5% (i.e. probability of declaring the regimen warrants further study when the true CR is 5%) and a power of 82% (probability of declaring the regimen warrants further study when the true CR is 20%). The higher alpha and lower power used in this design reflect the intention to use this as a pilot trial.

Secondary Endpoints

For the secondary endpoints, 21 eligible patients will be sufficient to estimate the PFS and OS at a particular time point (e.g. 9 weeks) to within ±21.4% (95% confidence interval). However, since PFS is estimated only among patients who do not undergo resection, we will only be able to estimate the PFS to within ±21.9%, ±22.5%, or ±23.9% (95% confidence intervals) if the percentage of patients who undergo resection is 5%, 10%, or 20%, respectively.

d. Translational Medicine Objectives: The statistical analysis of the translational medicine objectives for Cohort B will be the same as for Cohort A except we will use CR as the endpoint instead of pCR.

To assess the hypothesis that higher mutational load is associated with CR rate, the study will assess the association between overall mutational load and CR rate. We will first calculate the per megabase mutation rate for each individual. Then we will use logistic regression to regress CR status on the mutation rates and use a 1-degree freedom likelihood ratio test to obtain a p-value for the association between response and mutation rate. We will control the type I error at the twosided alpha=0.05 level. We estimated the minimal detectable odds-ratio under the assumption that we will collect exome sequencing data on 21 patients and that we will control the type I error rate at the two-sided alpha=0.05 level. In prior data, the median number of mutations per megabase in desmoplastic melanoma was found to be 62 and the 25th and 75th percentiles were 33 and 101, respectively (private communication, [name] to [name], 11/18/2014). Therefore, by matching the quantiles, we approximate the distribution of the per megabase mutation rate across patients as a Weibull with shape parameter 1.4 and scale parameter 80. Assuming a baseline response rate of 5% we anticipate over 70% power to detect a log odds-ratio of 0.45 (corresponding to an odds-ratio of 1.57) for each 10 mutation increase in the per megabase mutation rate. If logistic regression is unstable or behaves poorly, e.g. due to low response rates, we will also consider robust and flexible alternatives such as the Wilcoxon test to compare mutation rates between responders and non-responders.

The study will examine whether change in T-cell infiltration following treatment is higher in the DM patients who respond. Specifically, we will compute the change in CD8 expression from baseline to progression and then compare the change between responders and non-responders using a two-sample t-test. We will control type I error at the alpha=0.05 level. Assuming that 20% of patients respond, then we anticipate 80% power to detect a difference in mean CD8 expression change 1.61 standard deviations. We will repeat the analysis comparing the change in CD8 expression from baseline to week 4 to determine whether T-cell infiltration in the on-treatment biopsy is associated with response at progression.

To assess the hypothesis that ctDNA fraction at baseline and week 4 are associated with response in DM patients, we will assess the association between response and ctDNA fraction using a two-sample t-test at the two-sided $\alpha = 0.05$ level. Assuming that 20% of patients respond, then we anticipate 80% power to detect a difference in mean ctDNA fraction of 1.61 standard deviations.

To assess the hypothesis that TCR clonality is higher in DM patients who respond, suggesting that the T-cells are targeting the tumor, we will compute the clonality metric as the normalized Shannon entropy for all patients at baseline, Week 4, and progression. We will then compute the change in clonality metric from baseline to progression. The change in clonality will be compared between responders and non-responders using a two-sample t-test with significance determined at the two-sided alpha=0.05 level. Assuming that 20% of patients respond, then we anticipate 80% power to detect a difference in clonality change of 1.61 standard deviations. We will repeat the analysis comparing the change in clonality from baseline to Week 4 to determine whether T-cell clonality in the on-treatment biopsy is associated with response at progression.

The study will examine adaptive immune resistance by first evaluating whether PD-L1 expression is increased at Week 4 and progression as compared to baseline using paired t-tests and controlling the type I error at the two-sided alpha=0.05 level. With 21 patients, we anticipate 80% power at each time point to detect a mean difference in expression of 0.64 standard deviations. We will further evaluate whether increased PD-L1 expression at Week 4 or at progression is

associated with response. Specifically, we will compute the change in expression from baseline to progression and then compare the change between responders and non-responders using a two-sample t-test. We will control type I error at the two-sided alpha=0.05 level. Assuming that 20% of patients respond, then at each time point we anticipate 80% power to detect a difference in mean PD-L1 expression change of 1.61 standard deviations. We will repeat the analysis comparing the change in PD-L1 expression from baseline to Week 4 to determine whether T-cell infiltration in the on-treatment biopsy is associated with response at progression. In addition to our assessment of overall mutational load, we will further conduct a neoantigen analysis. Specifically, we will predict the immunogenicity of each nonsynonymous somatic mutation using NetMHC. We will then use logistic regression to regress CR status on the number of predicted immunogenic mutations, computing a p-value using a 1-df test and controlling type I error at the two-sided alpha=0.05 level.

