10.2 Objective Status at Each Disease Evaluation

Objective Status is to be recorded at each evaluation. All measurable lesions up to a maximum of 2 lesions per organ 5 lesions in total, representative of all involved organs, should be identified as target lesions at baseline. All other lesions (or sites of disease) including any measurable lesions over and above the 5 target lesions should be identified as non-target lesions. Measurements must be provided for target measurable lesions, while presence or absence must be noted for non-target measurable and non-measurable disease.

For studies that use disease progression as an endpoint, whole body scanning at specific intervals is necessary to determine that progression is NOT present outside of the "target" areas. Therefore, in these studies it is not acceptable to image only the "target" areas of the body in follow-up scans. For study-specific imaging requirements, see the Study Calendar in Section 9.0.

- a. Complete Response (CR): Complete disappearance of all target and non-target lesions (with the exception of lymph nodes mentioned below). No new lesions. No disease related symptoms. Any lymph nodes (whether target or non-target) must have reduction in short axis to < 1.0 cm. All disease must be assessed using the same technique as baseline.
- b. Partial Response (PR): Applies only to patients with at least one measurable lesion. Greater than or equal to 30% decrease under baseline of the sum of appropriate diameters of all target measurable lesions. No unequivocal progression of non-measurable disease. No new lesions. All target measurable lesions must be assessed using the same techniques as baseline.
- c. Stable: Does not qualify for CR, PR, Progression or Symptomatic Deterioration. All target measurable lesions must be assessed using the same techniques as baseline.
- d. Progression: One or more of the following must occur: 20% increase in the sum of appropriate diameters of target measurable lesions over smallest sum observed (over baseline if no decrease during therapy) using the same techniques as baseline, as well as an absolute increase of at least 0.5 cm. Unequivocal progression of non-measurable disease in the opinion of the treating physician (an explanation must be provided). Appearance of any new lesion/site. Death due to disease without prior documentation of progression and without symptomatic deterioration (see Section 10.2e).

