- You are associated as an investigator or CRA/RN at the institution where the patient is being treated or followed,
 - Your Web User Administrator has added you as a web user and has given you the appropriate system permissions to view data for that institution.

For assistance with points 1 and 2 call the Operations Office at [name]. For point 3, contact your local Web User Administrator (refer to the "Who is my Web User Administrator?" function on the swog.org Members logon page).

For difficulties with the CRA Workbench, please email [contact].

- Institutions participating through the Cancer Trials Support Unit (CTSU), please refer to the CTSU Participation Table.
- 14.4 Data Submission Overview and Timepoints
 - a. WITHIN 7 DAYS OF INITIAL REGISTRATION, SUBMIT:

S1512 Onstudy Form

\$1512 Baseline Abnormalities Form

Baseline Tumor Assessment Form (RECIST 1.1)

Radiology reports from all scans performed to assess disease at baseline**

Physician report documenting any measurement of skin lesions made during a physical examination**

Pathology report documenting histologic confirmation of desmoplastic melanoma**

**NOTE: Upload reports via the Source Documentation: Baseline form in Rave®.

Whole blood specimens must be collected prior to starting protocol treatment and MUST BE SUBMITTED THE SAME DAY AS COLLECTED.

b. WITHIN 28 DAYS OF REGISTRATION:

See Section 15.0 for specimen submission requirements.

c. WITHIN 7 DAYS AFTER EACH CYCLE OF TREATMENT (1 CYCLE = 21 DAYS) SUBMIT:

S1512 Treatment Form

\$1512 Adverse Event Form

d. FOR COHORT A, WITHIN 7 DAYS AFTER THE END OF TREATMENT DISEASE ASSESSMENT:

Follow-Up Tumor Assessment Form (RECIST 1.1)

Radiology reports from all scans performed to assess disease*. Physician must note tumor measurement in patient records.

Physician report documenting any measurements of skin lesions made during a physical examination.*

NOTE: Upload reports via the Source Documentation: Follow-Up form in Rave®

FOR COHORT B, WITHIN 7 DAYS AFTER EACH DISEASE ASSESSMENT (SEE STUDY CALENDAR FOR SCHEDULE) UNTIL PROGRESSION* (AS DEFINED IN SECTION 10.2d), SUBMIT:

Follow-Up Tumor Assessment Form (RECIST 1.1)

Radiology reports from all scans performed to assess disease.* Physician must note tumor measurement in patient records.

Physician report documenting any measurements of skin lesions made during a physical examination.*

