*NOTE: Upload reports via the Source Documentation: Follow-Up form in Rave®.

f. WITHIN 7 DAYS OF DISCONTINUATION OF PROTOCOL TREATMENT, SUBMIT:

Off Treatment Notice

\$1512 Treatment Form

\$1512 Adverse Event Form.

g. WITHIN 14 DAYS OF PROGRESSION OR RELAPSE, SUBMIT:

Follow-Up Tumor Assessment Form (RECIST 1.1) OR Follow-Up Form (if patient underwent surgery to resect disease after starting protocol therapy).

Radiology reports from all scans performed to assess disease*. Physician must note tumor measurement in patient records.

Physician report documenting any measurements of skin lesions made during a physical examination.*

If patient was on protocol treatment at the time of progression, also submit the materials specified in Section 14.4f.

See Section 15.0 for specimen submission requirements.

*NOTE: Upload reports via the Source Documentation: Follow-Up form in Rave®.

h. WITHIN 14 DAYS OF SURGERY TO RESECT DISEASE, SUBMIT:

S1512 Pathologic Response Form

All operative and pathology reports from the procedure*.

Submit surgical specimen and specimen from biopsy between Weeks 3-5. See Section 15.0 for specimen submission requirements.

*NOTE: Upload reports via the Source Documentation: Follow-Up form in Rave®.

i. ONCE OFF ALL PROTOCOL TREATMENT SUBMIT EVERY 6 MONTHS FOR THE FIRST 2 YEARS, THEN YEARLY FOR A TOTAL OF 5 YEARS FROM INITIAL REGISTRATION:

Follow-Up Form

Late Effects Form (if prior to treatment for progression or relapse or a second primary, and prior to non-protocol treatment, the patient experiences any severe [Grade \geq 3] long term toxicity that has not been previously reported).

j. WITHIN 28 DAYS OF KNOWLEDGE OF DEATH:

Notice of Death **and all of the items listed in Section 14.4e** (if the patient was still on protocol treatment) or Follow-Up Form (if the patient was off protocol treatment) documenting death information.

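### Cohort B's primary complete-response endpoint has no cut-off at surgery, so complete surgical clearance can be scored as a response to pembrolizumab

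*Combined protocol and SAP*

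**What the plan says.** Section 11.2b gives the decision rule: "Three or more complete responses out of 21 would be considered evidence that the treatment warrants further study". The design takes 5% as uninteresting and 20% as of interest, with stated alpha 8.5% and power 82%. The rule also depends on toxicity and overall survival looking favourable, and the cohort is described as a pilot. Section 1.1b counts confirmed and unconfirmed CR.

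The CR status in Section 10.2a begins "Complete disappearance of all target and non-target lesions". It also requires no new lesions, no disease-related symptoms, lymph nodes below 1.0 cm in short axis, and assessment by the baseline technique. It does not say by what means the lesions must have gone. In Section 10.3, only progression or symptomatic deterioration closes the period in which a CR can be recorded.

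Section 7.2c allows surgery in Cohort B when disease becomes resectable. Section 7.3 states the aim of removing every disease site, and under Section 7.6 resection completes protocol treatment. Calendar 9.2 keeps CT or PET/CT in the post-treatment column, and footnote k runs it to progression. Section 14.4 requires the RECIST form as follows: "FOR COHORT B, WITHIN 7 DAYS AFTER EACH DISEASE ASSESSMENT (SEE STUDY CALENDAR FOR SCHEDULE) UNTIL PROGRESSION". Section 14.4g, which applies at progression or relapse, accepts a Follow-Up Form in its place "if patient underwent surgery to resect disease after starting protocol therapy".

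Section 11.2c addresses surgery for a secondary endpoint: "since PFS is estimated only among patients who do not undergo resection". For Cohort A, Section 11.1b counts patients who are incompletely resected or not operated on as non-responders. Section 11.2b has no rule for resected patients.

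**The concern.** The Cohort B rule is meant to judge pembrolizumab. If a patient responds partially, is resected to no visible disease and is then rescanned, the scan shows what surgery and drug achieved together. Nothing in Sections 10.2, 10.3 or 11.2b prevents that scan from being recorded as CR.

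The threshold is only three, so one or two such patients matter. CR also defines responders in Cohort B's translational comparisons (Section 11.2d), so a misclassified patient would carry into those.

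The silence leaves a second choice open. An analyst could follow the PFS approach and drop resected patients from the CR denominator. That also departs from the stated design, and the choice could be made after the results are known.

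**Working it through.** **1. The plan's own figures.** Inputs from Section 11.2b are n = 21, threshold 3, p0 = 0.05 and p1 = 0.20.
- Alpha = P(Bin(21, 0.05) ≥ 3) = 0.0849, stated as 8.5%.
- Power = P(Bin(21, 0.20) ≥ 3) = 0.8213, stated as 82%.

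Both reproduce. The arithmetic is sound, and the gap lies in the endpoint definition.

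**2. What the resection rates in Section 11.2c are.** The half-width 1.96 × √(0.25/n), with n = 21, 19.95, 18.9 and 16.8 (0%, 5%, 10% and 20% resected), gives 21.4%, 21.9%, 22.5% and 23.9%, as stated. The rates are conditional scenarios for PFS precision, not forecasts.

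**3. How many post-operative scans are needed.** Sections 10.3b and 10.3c decide this.
- No PR status at least four weeks earlier: one post-operative CR status is an unconfirmed CR, which counts under Section 1.1b.
- A PR status at least four weeks earlier: PR followed by one CR status is two statuses of PR or better, so best response is PR. A second CR status at least four weeks after the first is then needed. Scans nine weeks apart satisfy that interval.

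**4. Effect by count.** Suppose k patients without a drug CR are scored CR after surgery, and the other 21 − k respond at 5%. The chance of meeting the threshold is P(Bin(21 − k, 0.05) ≥ 3 − k).
- k = 1: P(Bin(20, 0.05) ≥ 2) = 1 − 0.95^20 − 20 × 0.05 × 0.95^19 = 0.264.
- k = 2: P(Bin(19, 0.05) ≥ 1) = 1 − 0.95^19 = 0.623.
- k = 3: the threshold is met by surgery alone.

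**5. Effect by rate.** Let r be the resection rate (Section 11.2c scenarios) and f the share of resected patients then scored CR. The documents give no value for f, so a range is shown. Resection is taken as independent of drug CR, so p = 0.05 + 0.95 × r × f. Cells are P(Bin(21, p) ≥ 3).

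| f (assumed) | r = 5% | r = 10% | r = 20% |
|---|---|---|---|
| one quarter | 13.7% | 19.9% | 33.7% |
| one half | 19.9% | 33.7% | 60.5% |
| all (upper bound) | 33.7% | 60.5% | 91.0% |

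**6. If resected patients were dropped instead.** With four resected (20% of 21 is 4.2), the rule becomes 3 of 17: alpha 5.0%, power 69.0%.

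**7. With a cut-off at surgery and a fixed denominator of 21.** The null CR rate cannot exceed 5%, so alpha stays at or below 8.5%. Power is 82.1% if no would-be CR is lost to surgery. If losses are proportional to resection (an assumption), p = 0.20 × (1 − r) = 0.19, 0.18 and 0.16, and power is 79.1%, 75.6% and 67.6%.

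**The case against.** The best counter-argument is that the authors meant RECIST scoring to end at surgery. Resection completes protocol treatment (Section 7.6), surgery triggers a Pathologic Response Form (14.4h), patients off treatment send Follow-Up Forms (14.4i), and 14.4g lets a resected patient report relapse without a RECIST form. It would be odd to require RECIST forms for each clear scan and then waive them at relapse. This is fair evidence of intent, but it does not close the gap. Section 14.4g acts only at progression or relapse, when the CR period is already over. Section 14.4i adds a form without withdrawing the one due after each assessment. No text sets a surgical cut-off for CR.

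Three stronger readings are tempting, and the documents do not support them.
- A reader might infer that one clear post-operative scan always makes a CR. Section 10.3 scores a patient with a PR at least four weeks earlier as PR until a second qualifying CR status.
- A reader might infer that every resected patient becomes a CR. Residual disease, new lesions or disease-related symptoms rule it out under Section 10.2a, and in a cohort that includes metastatic disease many resections may not clear everything.
- A reader might infer that the plan expects 5% to 20% resected and that its true error rate is 34% to 91%. The rates are illustrative, and those figures need every resected patient to be scored CR.

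Reaching 3 of 21 is also not automatic success, since toxicity and survival must look favourable.

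**Conclusion.** The concern holds as a gap in the endpoint definition. As written, the rules allow complete surgical clearance to be scored as CR in Cohort B's primary endpoint. The 8.5% alpha is correct only if no such patient is counted.

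The firmest measure is by count: at a true drug CR rate of 5%, one surgical CR among 21 raises the chance of meeting the threshold from 8.5% to 26%, and two raise it to 62%. The figures by resection rate rest on an assumed share scored CR and on independence of resection and drug response. They are a range, not a prediction. None is a probability that the regimen will be declared worth pursuing.

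The documents do not show that the authors intended to credit surgery to the drug. The omission should be corrected, and it does not invalidate the design.

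**What to change.** Add to Sections 11.2b and 10.3, for Cohort B's primary endpoint:
- Only objective statuses dated before therapeutic resection of disease count toward best response. A diagnostic biopsy to clarify a residual lesion under Section 10.2g.7 is not a resection for this purpose.
- Patients resected without a prior CR remain in the denominator of 21 as non-responders.

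Report pathologic response in resected Cohort B patients separately, so that good outcomes after surgery remain visible. Settle the wording before the CR count is tabulated.

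This changes the analysis only. Operative and pathology reports, and the reports of disease assessments, are already collected under Section 14.4, so no new data are needed. The cost is that patients who might have reached CR without surgery count as failures, with the loss of power shown in step 7 of the working. The biopsy exception matters because a rule that voided every status after removal of any lesion could discard a genuine drug CR.

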1.2 Secondary Objectives

Cohort A

- a. To estimate the 9 week response rate (RR) (unconfirmed complete and partial responses) among patients with measurable disease.
- b. To estimate the median overall survival (OS).
- c. To evaluate safety and tolerability of pembrolizumab (MK-3475) in the neoadjuvant setting.

Cohort B

- a. To estimate the median progression-free survival (PFS).
- b. To estimate the median overall survival (OS).
- c. To evaluate safety and tolerability of pembrolizumab (MK-3475) in this setting.
- 1.3 Other objectives (all patients)
 - a. To evaluate the hypothesis that higher mutational load in the patient derived baseline tumor biopsy samples is associated with higher pathologic complete response (pCR).
 - b. To evaluate T cell infiltration into the tumors and circulating tumor DNA profile from blood samples in DM patients and correlate with response to PD-1 blockade.
 - c. To evaluate the clonality of tumor infiltrating T cells in DM patients and correlate with response to PD-1 blockade.
 - d. To evaluate adaptive immune resistant mechanism in DM tumors.

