Desmoplastic melanoma (DM) is a difficult tumor to remove surgically. (9) Frequently there is extensive perineural spread and surgery ends up being quite extensive with poor local control. Many times, these lesions present as small primaries only to find intraoperatively that they extend well beyond what is seen clinically or in imaging. (10,11) Patients are left with significant surgical deficits in the face of locally progressive disease. Due to the difficulty in gaining local control surgically, this study will offer patients with measurable desmoplastic melanoma treatment with pembrolizumab (MK-3475).

Patients with desmoplastic melanoma, locally advanced or metastatic, will be eligible to receive therapy on the trial. This will enhance the accrual rate. The primary end point of ORR after 3 cycles will normalize the data between the two groups while allowing for subsequent clinical intervention (ie surgery in those with locally advanced disease, or continued treatment in those with metastatic disease). The secondary endpoints of PFS and OS will also be collected for both groups. For individuals undergoing resection, this study will obtain data on the pCR and the ability to obtain clean margins. This study will evaluate tissue samples for mutational load and determine if the higher mutational load is associated with the ORR, in search of potential markers predictive of response. Tissue will also be evaluated for T cell infiltration, the clonality of tumor infiltrating T cells, and adaptive immune resistant mechanisms.

This trial hypothesizes that immune responses after administering pembrolizumab (MK-3475) will be also focused on neoepitopes resultant from somatic mutations, and that melanoma subsets with the highest mutational loads should have higher response rates than unselected melanomas. Among all melanomas, desmoplastic melanoma is a subset with a strong link to chronic UV exposure and high mutational load.

There are no prospective studies evaluating the response of desmoplastic melanoma to biologic therapies. This study has the potential to change the course of therapy for those with locally advanced disease, to improve overall survival in individuals with desmoplastic melanoma, and to obtain data that, if favorable, can be used further to determine predictive value of PD1 blockade with pembrolizumab (MK-3475).

Inclusion of Women and Minorities

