- If at any time after the first disease assessment the patient's disease is deemed to be unresectable, treatment will continue for 1 more cycle and a repeat disease assessment, using the same techniques as baseline, must be obtained 4 weeks (Day 28 +/- 7 days) later. If, after this second disease assessment the patient's disease is deemed to be resectable the patient must continue with resection as previously planned. Patients who do not undergo a second disease assessment following an initial documentation of progression will be considered failures. [Note: Most responses to pembrolizumab (MK-3475) will occur within 3 cycles, but a delayed response is also possible. If the patient has become unresectable after 3 cycles, one more cycle is given to capture those who might have a delayed response to therapy. If the delayed response is present, unresectable disease may become resectable].

c. Cohort B: Pembrolizumab (MK-3475) for unresectable disease

Patients in Cohort B will receive the following treatment for a maximum of 34 cycles or until the patient has met any of the criteria in Section 7.5, whichever is first.

Agent	Dose	Route	Schedule	
MK-3475 (pembrolizumab)	200 mg	IV over 30 minutes	Day 1, Q 3 weeks	

1 cycle = 21 days.

Pembrolizumab (MK-3475) treatment should be administered after all procedures and assessments have been completed and the patient is deemed eligible. Pembrolizumab (MK-3475) treatment may be administered up to 3 days before or after the protocol-specified Q 3 weeks due to administrative reasons.

Pembrolizumab (MK-3475) treatment will be administered on an outpatient basis.

Pembrolizumab (MK-3475) will be administered as a 30 minute IV infusion. Infusion timing should be as close to 30 minutes as possible; however, a window of -5 minutes and +10 minutes is permitted (*i.e.*, infusion time is 25-40 minutes).

 Disease assessments, using the same technique as baseline, must be performed every 3 cycles (9 weeks) for the first 6 months. Scans should then be obtained every 4 months. Tumor measurements are determined with

scans or if the only site of measurable disease is cutaneous, with photographically measurable disease.

- Patients whose disease becomes resectable in the opinion of the treating investigator, may have surgery which must be performed as described below in Section 7.2. Patient may choose to continue protocol therapy instead of surgical resection.

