- Patients may remain on protocol treatment after progression if they continue to derive clinical benefit in the opinion of the treating investigator.

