7.6 Criteria for Removal from Protocol Treatment – Cohort B

- a. Progression of disease (as defined in Section 10.0). However, patients may remain on protocol treatment after progression if they continue to derive clinical benefit in the opinion of the treating investigator.
- b. Disease becomes resectable and patient chooses to have surgical resection.
- c. Unacceptable toxicity
- d. The patient may withdraw from the study at any time for any reason.
- e. The investigator may discontinue treatment if they determine that the patient's continued treatment on the study is detrimental to their long-term health, or due to poor compliance with the study's required visits and treatments.
- f. Positive pregnancy test.
- Completion of protocol treatment (either resection or 34 cycles of pembrolizumab).

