7.9 Follow-Up Period

All patients will be followed until death or 5 years after initial registration, whichever occurs first.

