10.5 Progression-Free Survival

From date of registration to date of first documentation of progression or symptomatic deterioration (see Section 10.2e), or death due to any cause. Patients last known to be alive without report of progression are censored at date of last contact.

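### Cohort B PFS leaves out patients who are later resected, which selects on a post-registration event and does not match the Section 10.5 definition

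*Combined protocol and SAP*

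**What the plan says.** Section 11.2 (Cohort B, secondary endpoints) first gives a precision of ±21.4% for PFS and OS at a fixed time with 21 eligible patients. It then widens the PFS figure to ±21.9%, ±22.5% or ±23.9% if 5%, 10% or 20% of patients are resected, "since PFS is estimated only among patients who do not undergo resection". It gives no reason for the restriction and no sensitivity analysis.

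Other sections bear on this:

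- Section 5.1b requires Cohort B disease to be unresectable at entry.
- Section 7.2 allows surgery later: "Patients whose disease becomes resectable in the opinion of the treating investigator, may have surgery". Section 7.6b makes this a reason to leave protocol treatment: "Disease becomes resectable and patient chooses to have surgical resection".
- Section 10.5 defines PFS as running "From date of registration to date of first documentation of progression or symptomatic deterioration", or death from any cause. Patients alive without reported progression are censored at last contact. Resection is not mentioned.
- Section 1.2 lists median PFS as the first secondary objective for Cohort B, without restriction.
- Section 2.0 adds: "The secondary endpoints of PFS and OS will also be collected for both groups".

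**The concern.** Time zero is registration, but membership of the PFS set depends on a later event that reflects both response to treatment and patient choice. A patient who responds well enough to become operable, and accepts surgery, is deleted from the estimate together with all the progression-free time already accrued. What remains is PFS among patients who were never resected. That group cannot be identified at registration and is not the treated cohort.

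Two analysts, one working from Section 10.5 and one from Section 11.2, would use different populations for the same named endpoint. Section 11.2 treats the exclusion only as a loss of precision, 0.5 to 2.5 points on its own figures, and does not consider bias.

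The stakes are limited. Median PFS is descriptive and is not named in the Cohort B decision rule. The complete response criterion (3 or more of 21), OS and safety do not depend on it.

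**Working it through.** **Step 1: reproduce the plan's precision figures.** The worst-case binomial half-width is 1.96 × √(0.25/n), with n = 21 from Section 11.2 and n = 21 × (1 − r) when a share r is resected.

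| r | n | half-width | plan states |
|---|---|---|---|
| 0 | 21 | 21.4% | ±21.4% |
| 5% | 19.95 | 21.9% | ±21.9% |
| 10% | 18.9 | 22.5% | ±22.5% |
| 20% | 16.8 | 23.9% | ±23.9% |

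All four match. The arithmetic takes resected patients out of the denominator, as the wording says. In numbers of patients, r is about 1, 2 and 4 of 21.

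**Step 2: bounds on the bias.** Let S be the true PFS at a landmark in the whole cohort, and f the event-free share at that landmark among resected patients. The plan would report (S − r·f)/(1 − r). The documents give no value for S or f, so S = 50% is an assumption.

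| f | r = 5% | r = 10% | r = 20% |
|---|---|---|---|
| 1 (all event-free) | 47.4% | 44.4% | 37.5% |
| 0.75 | 48.7% | 47.2% | 43.8% |
| 0.5 (break-even) | 50.0% | 50.0% | 50.0% |
| 0.25 | 51.3% | 52.8% | 56.2% |
| 0 (all progressed) | 52.6% | 55.6% | 62.5% |

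Example for f = 1, r = 10%: (0.50 − 0.10)/0.90 = 44.4%.

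The f = 1 row is relevant at the plan's own example landmark of 9 weeks. Anyone resected after week 9 without earlier progression is event-free at week 9 by definition. The shift in that row is −r(1 − S)/(1 − r), so it shrinks as S rises. At an assumed S of 80% it is −1.1, −2.2 and −5.0 points, against −2.6, −5.6 and −12.5 at 50%.

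**Step 3: a neutral case.** Suppose surgery is given at random among patients still progression-free, has no effect on PFS, and a share s of the cohort is progression-free at that time. For a landmark after surgery, the reported value is S × (1 − r/s)/(1 − r).

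| s | r = 5% | r = 10% | r = 20% |
|---|---|---|---|
| 0.9 | 49.7% | 49.4% | 48.6% |
| 0.8 | 49.3% | 48.6% | 46.9% |
| 0.6 | 48.2% | 46.3% | 41.7% |

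Example for s = 0.6, r = 20%: 0.50 × (1 − 0.333)/0.80 = 41.7%.

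For exponential PFS, simulation with 2,000,000 draws gives these ratios of reported to true median:

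| s | r = 5% | r = 10% | r = 20% |
|---|---|---|---|
| 0.9 | 0.991 | 0.981 | 0.959 |
| 0.8 | 0.980 | 0.958 | 0.906 |
| 0.6 | 0.948 | 0.889 | 0.737 |

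The median is therefore understated by about 1–5%, 2–11% and 4–26%. On a time scale, with resection at week 18 (assumed), a true median of 6.0 months is reported as 5.7, 5.4 or 4.6 months, and a true 12.0 months as 11.7, 11.5 or 10.8.

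In this neutral case, censoring at resection instead of excluding returns 49.9–50.0% throughout. The bias there comes from the exclusion itself.

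**Step 4: direction.** Becoming resectable usually means not having progressed, which points to f above S and a downward bias. It is not guaranteed. Section 7.2 states "Patients may remain on protocol treatment after progression" if they still benefit, so a patient could progress, be resected later, and have that event deleted. A poor course after surgery also works the other way. With a base median of 12 months and a hazard that doubles after surgery at week 18, the reported median is about 0.1 to 0.2 months too high.

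**The case against.** The strongest reply is that this is a choice of estimand. After surgery the baseline target lesions can no longer be followed, Section 10.2f makes status unknown when target lesions are not assessed, and Section 14.4g moves resected patients from the RECIST tumor assessment form to a general follow-up form. Keeping everyone mixes RECIST progression with relapse after surgery. That is a fair reason to handle resection explicitly, and it could support censoring at resection. It does not support deleting the patient's time before surgery.

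Other points stand in part:

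- Section 10.5 names no analysis population and nowhere says that resected patients are included. The mismatch is a restriction in Section 11.2 that Sections 10.5 and 1.2 do not carry, not two opposed statements.
- The half-width formula has no term for censoring, so the arithmetic alone cannot separate exclusion from a conservative allowance for censoring. The plan's wording settles it.
- The Section 2.0 sentence is weak support. It speaks of collecting PFS, and the same paragraph names a primary endpoint that differs from Section 1.1.
- The restriction is stated openly, concerns about 1 to 4 patients, and affects a descriptive endpoint in a pilot. The largest illustrated median shift, 26%, needs a third of all progression-free patients to be resected (20%/60%).

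These points limit the importance. They do not remove the selection on a future event.

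**Conclusion.** The concern holds. Section 11.2 defines the PFS population by an event that occurs after the PFS clock starts, and the result does not estimate PFS in the treated Cohort B. The bias is probably downward. The size depends on assumed values: a 50% landmark PFS, the plan's resection scenarios, and for the neutral case 60–90% progression-free at surgery and exponential PFS for the medians. At 5% and 10% resected, the landmark shift is at most 5.6 points in either direction, small against ±21.4%. At 20% resected it ranges from −12.5 to +12.5 points at the extremes, and from −8.3 to −1.4 points in the neutral case. The mismatch between sections stands whatever the size. It should be fixed, but it does not touch the primary complete response rule, OS or safety.

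**What to change.** - **Section 11.2:** estimate PFS in all eligible Cohort B patients from registration, as Section 10.5 defines it. Delete the restriction to non-resected patients and the ±21.9%, ±22.5% and ±23.9% figures. State ±21.4%.
- **Section 10.5:** add a sentence that the first relapse or new lesion after resection counts as progression, dated from the data reported under Section 14.4g. Section 10.2d already counts a new lesion or site as progression, so this mainly makes the handling after surgery explicit.
- **Sensitivity analysis:** censor at the date of resection, with a caveat that this censoring is likely to be informative, because surgery goes to patients whose disease has become resectable. The unbiased result in Step 3 relies on surgery being random among progression-free patients.
- **Supplementary:** label any estimate in non-resected patients only as such.

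**Cost:** text changes only, with no new visits, scans or forms. Section 7.9 states "All patients will be followed until death or 5 years after initial registration" (whichever comes first), and Section 14.4g already collects relapse after surgery with radiology reports. Study Calendar 9.2 schedules visits and imaging before progression, but footnote k (every 9 weeks until progression) and footnote y with Section 7.2 (every 9 weeks for 6 months, then every 4 months) differ on the interval and should be reconciled. The remaining downside is that the main estimate then reflects pembrolizumab plus any later surgery. The censoring analysis helps with that, subject to its caveat.
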